Participants will be randomized into either a ketogenic diet arm or a mixed diet with ketone ester arm. During the first 2 weeks, participants will be provided food meeting either the Ketogenic diet requirements, or mixed diet (following the USDA dietary macronutrient recommendations) at a caloric level estimated at 100% of energy requirements. The participants randomized into the Mixed diet arm will also receive a ketone ester supplement. This will be provided throughout the study. Energy requirements will be determined using a combination of information obtained from testing including habitual diet assess through an NIH sponsored food frequency questionnaire (e.g., DHQ-III which will be sent to the participants email) , body mass and composition, and formulas (e.g., Harris-Benedict) that consider sex, age, height and activity patterns.

All participants will be provided all their meals and snacks selected to meet all calorie needs via individualized pre-ordered groceries and/or prepared food for the first 2 weeks of the diet. We have established the infrastructure for conducting controlled feeding studies for other funded research including development and implementation of 7-day

rotational menus, hybrid feeding approaches (providing groceries), and use of ready-

Primary	Changes in anovulatory status in women with PCOS
Secondary	
Changes in reproductive hormones such as progesterone, estrogen, LH, FSHAnalysis of potential predictive metabolic baseline characteristicsDifferences in blood metabolites (metabolic and lipids).
Exploratory	
Examine cardiovascular function and ovarian morphology using magnetic resonance imaging (MRI).

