Through this robust analytical strategy, we aim to unravel the influence of a ketogenic dietary intervention on menstrual cycle regularity and ovulation patterns in women with PCOS, thereby providing a compelling narrative around the potential benefits of a ketogenic diet.

STUDY MONITORING

Concomitant Medication/Supplements and Treatment

All concomitant medications/supplements used 1 months prior to Screening Visit and during the study will be reported to the study personnel for assessment and recorded in the participant's study documents.

Radiation

This study comprises two, whole-body DXA scans, eight-weeks apart. This radiation exposure is not necessary for medical care and is for research purposes only. The total amount of radiation is about 78 mrem and is approximately equivalent 95 days of exposure to natural background radiation. This procedure involves minimal risk and is necessary to obtain the research information about changes in lean body mass, fat mass, and bone density (i.e., 3-compartment assessment model).

Adverse Event Monitoring

An AE is defined as any untoward medical occurrence in an investigation participant following written informed consent that does not necessarily have a causal relationship with the study product. An AE can be any unfavorable or unintended sign (including an abnormal finding), symptom, or disease temporally associated with the use of an investigational product, whether or not related to the investigational product. This includes any occurrence that is new in onset or aggravated in severity or frequency from the baseline condition, or abnormal results of diagnostic procedures (including laboratory test abnormalities).

Some side effects or GI symptoms could occur as an outcome of these dietary interventions; side effects listed in the beverage tolerability questions and reported will not be categorized as AEs but recorded as study outcomes. Side effects, outside of what is expected as a result of study product consumption, reported by participants and judged by the Investigators as medically relevant events and related to study product will be recorded as AEs.

Events should be considered AEs if they:

- Result in discontinuation from the study,
- Require treatment or any other therapeutic intervention,
- Require further diagnostic evaluation (excluding a repetition of the same procedure to confirm the abnormality),

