- Are associated with clinical signs or symptoms judged by the Investigator to have a significant clinical impact.

Grading and Severity

The Investigator will evaluate all AEs with respect to their severity, and record the outcome and action taken on the AE study documents . AEs will be graded as:

Mild: Awareness of symptoms but easily tolerated

Moderate: Discomfort enough to interfere with but not prevent daily activity

Severe: Unable to perform usual activity

Relationship

The Investigator will also judge the likelihood that the AE was related to the study beverage and document this on the appropriate study documents as:

NOT RELATED	This category applies to those adverse experiences which, after careful consideration, are clearly and incontrovertibly due to extraneous causes (disease, environment, etc.).
UNLIKELY	In general, this category can be considered applicable to those experiences that after careful medical consideration at the time they are evaluated, are judged to be, unlikely related to the study beverage.
POSSIBLY	This category applies to those adverse experiences for which, after careful medical consideration at the time they are evaluated, a connection with the study beverage administration appears possible but cannot be ruled out with certainty.
PROBABLY	This category applies to those adverse experiences that, after careful medical consideration at the time they are evaluated, are felt with a high degree of certainty to be related to the study beverage.
DEFINITELY	This category applies to those adverse experiences which, the Investigator feels are incontrovertibly related to the study beverage.

Appropriate therapeutic action and follow-up measures will be performed by the Investigator in accordance with appropriate medical practice standard of care.

Serious Adverse Event Definition/Qualification

A SAE is defined as an AE that results in any of the following outcomes:

- Death (note that death is the outcome of a SAE and the cause of death should be listed as the AE),
- Life-threatening event,
- In-patient hospitalization or prolongation of existing hospitalization,
- A persistent or significant disability/incapacity,
- Congenital anomaly or birth defect,

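### Relatedness of adverse events is judged only against an undefined study beverage, so harm caused by the ketogenic diet cannot be graded as related

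*Protocol*

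**What the plan says.** The Diet Intervention section sets the comparison: "Participants will be randomized into either a ketogenic diet arm or a mixed diet with ketone ester arm". It adds: "The participants randomized into the Mixed diet arm will also receive a ketone ester supplement". The ester is supplied throughout the study. No drink or supplement is described for the ketogenic arm. The Sample Size paragraph plans 20 participants per arm, 40 in all.

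Adverse Event Monitoring expects harm from the diets themselves: "Some side effects or GI symptoms could occur as an outcome of these dietary interventions". The Relationship section, however, gives causality a different object: "The Investigator will also judge the likelihood that the AE was related to the study beverage". The three positive categories follow suit. POSSIBLY applies where "a connection with the study beverage administration appears possible but cannot be ruled out with certainty", PROBABLY to events that "are felt with a high degree of certainty to be related to the study beverage", and DEFINITELY to events that "the Investigator feels are incontrovertibly related to the study beverage". UNLIKELY is also worded against the beverage. NOT RELATED names no beverage and is kept for events "clearly and incontrovertibly due to extraneous causes (disease, environment, etc".

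The same term returns in the last stop criterion under Serious Adverse Event Follow-Up and in the third reason under Withdrawal of Participants from the Study.

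**The concern.** A causality scale has to point at what the trial assigns. This one points at an item that the protocol does not define and that, on its own description, half of the participants do not receive. An investigator who follows the wording has no positive grade for an event caused by the ketogenic diet, the intervention that the statistical plan sets out to evaluate. An investigator who silently reads beverage as intervention will grade the same event differently. The causality record then depends on the reader.

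At stake is the only graded causality scale in the protocol. Safety is not a listed primary, secondary or exploratory outcome, but the Impact section hopes to support the approach as safe as well as effective and to inform a fully powered trial. A record that shifts diet-caused events towards unrelated is a poor basis for that.

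**Working it through.** No calculation underlies this point. The check counts the terms and then applies the categories as written.

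**1. Where the terms occur**
- Study beverage: 5 times in Relationship (the instruction, UNLIKELY, POSSIBLY, PROBABLY, DEFINITELY), once in Serious Adverse Event Follow-Up and once in the withdrawal rules. 5 + 1 + 1 = 7. It never occurs in the sections that describe the design, interventions, methods or analysis.
- Study product: 3 times, and investigational product: 2 times, all in Adverse Event Monitoring. Neither is defined, and the relatedness scale uses neither.
- Adverse Event Monitoring also mentions beverage tolerability questions. The survey note to the procedures table lists only menstrual history and Ferriman-Gallwey, and the Methods add a satiety scale. No tolerability questionnaire is described.

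**2. What the beverage could be**
The only candidate is the ketone ester, which is never called a beverage. It goes to the mixed-diet arm: 20 of 40 participants.

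**3. An AE caused by the ketogenic diet, category by category**

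| Category | Needs | Available as written? |
|---|---|---|
| NOT RELATED | a clearly extraneous cause | Not naturally: a diet assigned by the protocol is not like disease or environment |
| UNLIKELY | unlikely link to the beverage | Yes, but it records a diet-caused event as unlikely related |
| POSSIBLY | possible link to the beverage | No, none is given in this arm |
| PROBABLY | link to the beverage, with high certainty | No |
| DEFINITELY | incontrovertible link to the beverage | No |

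The beverage is named in 4 of 5 categories and in 3 of 3 positive ones. The event ends up as UNLIKELY, or as NOT RELATED if the diet is regarded as extraneous to the beverage. Both are wrong as a statement about the assigned intervention.

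**4. The mixed-diet arm**
Taking the ester to be the beverage, a participant receives it alongside the diet for the whole study. An ester effect can seldom be separated from a diet effect, so POSSIBLY is usually open. The scale fails here only when the event is known to come from the diet and not the ester.

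**5. Secondary places**
- SAE follow-up: 1 of the 5 stop criteria names the beverage. It allows follow-up to end when the event is attributed to something other than the beverage, or other than the conduct of the study. The second limb makes it unclear whether a diet-caused serious event would qualify.
- AE recording: Adverse Event Monitoring defines an AE regardless of relatedness, then records certain side effects as AEs only if they are judged related to the study product. The two sit badly together. An event that meets any of the four listed criteria in that section is still an AE.

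**The case against.** The strongest defence is that the beverage is carried-over template wording and that any sensible investigator will read it as the study intervention. There is some support in the text. The withdrawal rule speaks of evaluating the beverage's effect, and what this trial evaluates is the diets. Adverse Event Monitoring also moves between dietary interventions, beverage and study product as if they were interchangeable. This makes the benign reading plausible. It does not remove the fault, because the protocol nowhere says so and the scale is an operative instruction.

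Three stronger readings might be inferred, and the protocol does not support them.
- *The scale fails equally in both arms, for all 40 participants.* It does not: with the ester given throughout, POSSIBLY would usually be available in the mixed-diet arm.
- *Follow-up of diet-caused serious events will be cut short.* The stop criterion also names study conduct, which plausibly covers an assigned diet. The protocol separately requires follow-up measures to the standard of care, prompt efforts to obtain follow-up information, and a 30-day entry for AEs ongoing at the final visit. The wording is ambiguous, not a rule to stop.
- *Diet-caused AEs will go unrecorded.* Events that meet a listed criterion remain AEs, and Recording of Adverse Events requires all AEs to be recorded.

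It is also fair to say that little else depends on the grade. Reporting of serious events to the IRB, severity grading and withdrawal for medical reasons do not use it, and the protocol plans no between-arm comparison of related AEs.

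**Conclusion.** The point stands for the ketogenic arm: 20 of 40 planned participants are under a scale that, as written, has no positive grade for harm caused by their intervention. In the mixed-diet arm it is limited to events known to come from the diet alone. The SAE stop criterion and the relatedness condition for recording AEs are secondary wording faults.

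The conclusion rests on two assumptions: that the ketone ester is the only thing the beverage could mean, and that the categories are applied as worded. If every investigator read beverage as intervention, the grades would be right, but only by a convention the protocol does not state. The number of misgraded events is not estimated, since no AE rate is given. The wording should be corrected: it is an operative safety rule that gives a wrong causality record when followed.

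**What to change.** Define one term, for example *assigned study intervention (ketogenic diet, or mixed diet plus ketone ester) or study procedures*, and use it in place of study beverage, study product and investigational product in Adverse Event Monitoring, Relationship and Serious Adverse Event Follow-Up. In the withdrawal rule, refer to the *effect of the assigned study intervention*. Reword the last SAE stop criterion to *attributed to a cause other than the assigned intervention and study procedures*. In Adverse Event Monitoring, drop relatedness as a condition for recording an AE.

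The cost is one wording amendment and possibly a few more AE entries. It needs no new visits, samples or participants.
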